### 8.2.3 Prior and Concomitant Medications

Medications will be coded using the World Health Organization Drug Dictionary Enhanced (WHODDE) and categorized as follows:

For Parts 1 [REDACTED]

**Prior medication:** any medication that started before the first dose date of study drug, regardless of when the medication ended.

**Concomitant medication:** medication continued or newly received on or after the first dose date of study drug through the end of the TE period.

**Post-treatment medication:** medication continued or newly received after the TE period.

For Part 2:

**Prior medication:** any medication that started before the first dose date of study drug in the Run-in Period, regardless of when the medication ended.

**Concomitant medication during the Run-in Period:** medication continued or newly received on or after the first dose date of study drug during the Run-in Period through the end of the TE period for the Run-in Period.

**Concomitant medication during the Treatment Period:** medication continued or newly received on or after the first dose date of study drug during the Treatment Period through the end of the TE period for the Treatment Period.

**Post-treatment medication:** medication continued or newly received after the TE period.

A given medication may be classified as follows: prior, concomitant, post-treatment, both prior and concomitant, both concomitant and post-treatment, or prior, concomitant, and post-treatment. In Part 2, concomitant may be concomitant during the Run-in Period, or concomitant during the Treatment Period, or both.

If a medication has a completely missing or partially missing start/stop date and it cannot be determined whether it was taken before the first dose date of study drug, concomitantly, or after the TE period, it will be classified as prior, concomitant, and post-treatment.

Prior medications and concomitant medications will be summarized descriptively using frequency tables by preferred name.

Summaries of medications will be based on the FAS, and presented by treatment group and overall for each part.

Post-treatment medications will be listed by subject.

Details for imputing missing or partial start and/or stop dates of medication are described in Appendix C.

#### **8.2.4 Study Drug Exposure**

Study drug exposure (in days) will be calculated as: last dose date of study drug – first dose date of study drug + 1 day, regardless of study drug interruption, and will be summarized descriptively. Study drug exposure will be summarized for the overall study drug period, which includes the Run-in Period, Treatment Period and Washout Period for Part 2, and the Treatment Period for Parts 1 [REDACTED]. Further, study drug exposure for the combined Treatment Period and Washout Period in Part 2 will also be summarized descriptively.

Study drug exposure (in weeks) will be summarized descriptively by the number of subjects (n), mean, SD, SE, median, min, and max. It will also be summarized in categories:  $\leq 2$  weeks,  $>2 - \leq 4$  weeks, and  $>4$  weeks (for Parts 1 and 2); and  $\leq 2$  weeks,  $>2 - \leq 4$  weeks,  $>4 - \leq 8$  weeks,  $>8 - \leq 12$  weeks, and  $>12$  weeks (for Part 4), using counts and percentages. Additionally, the total study drug exposure, defined as the sum total of the study drug exposure across all subjects (in patient-weeks), will be provided.

Exposure summaries will be based on the Safety Set, and presented by treatment group and overall, for each part. For Part 2, exposure summaries will be based on the Safety Set for the Treatment Period.

#### **8.2.5 Study Drug Compliance**

Percentage of tablets taken will be calculated as:  $100 \times [(total\ number\ of\ tablets\ dispensed) - (total\ number\ of\ tablets\ returned)] / (total\ number\ of\ tablets\ planned\ to\ be\ taken\ per\ day \times duration\ of\ study\ drug\ exposure\ in\ days)$ . The maximum percentage of tablets taken will be 100%.

Study drug compliance will be calculated as:  $100 \times [1 - (total\ number\ of\ days\ of\ study\ drug\ interruption) / (duration\ of\ study\ drug\ exposure\ in\ days)]$ . A study drug interruption on a given day will be determined by an interruption of all drugs on that day.

Percentage of tablets taken and study drug compliance will be summarized descriptively by the number of subjects (n), mean, SD, SE, median, min, and max. It will also be summarized in categories:  $<80\%$  and  $\geq 80\%$  using frequency tables.

For all parts, study drug compliance will be summarized for the Treatment Period only. Similarly, for all parts, percentage of tablets taken will be summarized for the Treatment Period only.

Percentage of tablets taken and study drug compliance summaries will be based on the FAS, and presented by treatment group and overall, for each part.

#### **8.2.6 Important Protocol Deviations**

An important protocol deviation (IPD) is a deviation that may significantly affect the completeness, accuracy, or reliability of the study data or that may significantly affect a subject's rights, safety, or well-being. IPD rules will be developed and finalized before database lock.

The protocol deviations that should be considered as potential IPDs include, but are not limited to:

- Subject was enrolled in the study despite the violation of inclusion/exclusion criteria
- Subject was less than 80% compliant with study drug based on number of tablets taken
- Subject received prohibited concomitant medications
- Subject received the wrong treatment or incorrect doses
- Subject remained in the study despite meeting withdrawal criteria

Occurrence of any of these events should be considered as potential IPDs, but a blinded team should categorize them as IPDs only if they have the potential to significantly affect the completeness, accuracy, or reliability of the study data or that may significantly affect a subject's rights, safety, or well-being.

IPDs will be provided in an individual subject data listing for each part. Additionally, IPDs (from the clinical database or from the site deviation log) will be summarized descriptively based on the FAS and presented by treatment group [REDACTED]. Details of the IPD rules are provided in Appendix D.

### **8.3 Efficacy Analysis**

All efficacy analyses described in this section will be based on the FAS, unless otherwise specified. TC groups with TEZ 100 mg qd (Cohort 1A) and 50 mg q12h (Cohort 1B) for the same dose of VX-440 will be pooled for the primary model-based analysis of all efficacy and pharmacodynamic (PD) variables in Part 1. [REDACTED]

Treatment groups TC-1A and TC-1B-low in Part 1 will be presented both pooled and separately, for descriptive analysis.

The placebo group will include subjects from all cohorts within a part, for all analyses. The analysis will include all available measurements through the last scheduled on-treatment visit including measurements after treatment discontinuation, per the visit windowing rules described in Appendix B. The post-dose measurements on the same day will not be used for any model-based analyses, but only reported in descriptive analyses.

#### **8.3.1 Primary Efficacy Variable**

The primary efficacy variable is the absolute change from baseline for pre-dose percent predicted FEV1 (in percentage units) through Day 29 in Parts 1 and 2, [REDACTED]

The percent predicted FEV1 is the ratio of FEV1 (L) to the predicted FEV1 (L), expressed as a percentage. The predicted FEV1 will be calculated using the Quanjer GLI-2012 Regression Equations and Lookup Tables, adjusting for age, height, sex and geographic region. Details are provided in Appendix E.

### **8.3.1.1 Primary Analysis of the Primary Efficacy Variable**

#### **8.3.1.1.1 Parts 1 and 2**

The null hypothesis to be tested is that the mean absolute within-group change from baseline in percent predicted FEV1 (ppFEV1) through Day 29 is zero for VX-440 in triple combination (TC) with TEZ/IVA, for each part, separately. A 2-sided *p*-value of 0.05 or less will be interpreted as sufficient evidence to reject the null hypothesis.

[figure not shown]
The primary analysis will be performed using a mixed-effects model for repeated measures (MMRM) with change from baseline in ppFEV1 as the dependent variable for each part, separately. This MMRM analysis will include all treatment groups within a part. For Part 1, the analysis will include 3 treatment groups: placebo, pooled TC-1A and TC-1B-low, and TC-1B-high. For Part 2, the analysis will include 2 treatment groups: placebo + TEZ/IVA, and TC-2 (VX-440 + TEZ/IVA). The model will include treatment group, visit, and treatment-by-visit interaction as fixed effects, with the continuous baseline ppFEV1 as a covariate, and will include all data from each treatment group and visit in the analysis. The model will be estimated using restricted maximum likelihood. Denominator degrees of freedom for the F test for fixed effects will be estimated using the Kenward-Roger approximation. An unstructured covariance structure will be used to model the within-subject errors. If the model estimation does not converge, a reduced compound symmetry covariance structure will be used instead. Conditional on the observed data and covariates, missing ppFEV1 data due to treatment or study discontinuation will be assumed to be missing at random; consequently, no imputation of missing data will be performed.

The adjusted means and 95% confidence intervals (CI) of the average treatment effect through Day 29 (Day 15 and Day 29 only) for each triple combination, with a 2-sided *p*-value will be estimated within MMRM using PROC MIXED in SAS, for all within-treatment and between-treatment comparisons, for each part, separately. Contrasts based on the fixed effects in the model, defined at the baseline covariate mean for the combined treatment groups using unique subjects in the FAS who have at least one post-baseline measurement through Day 29, will be used to estimate the average treatment effect across post-baseline visits through Day 29.

[figure not shown]
Further, the adjusted mean and 95% CI of the treatment difference between each triple combination and placebo at each post-baseline visit through Day 29 will be provided along with the corresponding *p*-value, for each part. In addition, the adjusted mean and 95% CI of the within-treatment difference at each post-baseline visit through Day 29 for each treatment group will be provided along with the *p*-value, for each part.

The adjusted mean (with 95% CI) obtained from the MMRM analysis at each post-baseline visit through Day 29 will be plotted by treatment group, for each part. In addition, a waterfall plot showing the subject-level absolute change in ppFEV1 at Day 29 will be presented, by treatment group. The plots will be based on the pooled treatment groups for Part 1.

In addition, for each part, descriptive analyses of the change from baseline will be performed for all treatment groups by post-baseline visit through the safety follow-up visit. Treatment groups in Part 1 will be presented both with TC-1A and TC-1B-low pooled, and separately for descriptive analysis.

**8.3.2 Analysis of Secondary Efficacy Variables**

The secondary efficacy variables include:

- Relative change in ppFEV1 from baseline through Day 29 (Parts 1 and 2) [REDACTED]  
[REDACTED]

- Absolute change in the CFQ-R respiratory domain score from baseline at Day 29 (Parts 1 and 2) [REDACTED]

[REDACTED]

[REDACTED]

[REDACTED]

[REDACTED]

[REDACTED]

The primary analysis of the secondary efficacy variables will pool treatment groups TC-1A and TC-1B-low in Part 1.

### 8.3.2.1 Relative change in ppFEV1 from baseline through Day 29 (Parts 1 and 2) [REDACTED]

#### Parts 1 and 2

The relative change in ppFEV1 from baseline through Day 29 is defined in Section 8.1. Analysis of this variable will be based on an MMRM model, similar to the primary analysis of the primary efficacy variable in Parts 1 and 2. The tabular presentation of results will also be similar

[REDACTED]

### 8.3.2.2 Absolute change in the CFQ-R respiratory domain score from baseline at Day 29 (Parts 1 and 2) [REDACTED]

[figure not shown]
[REDACTED]

#### Parts 1 and 2

The absolute change in the CFQ-R respiratory domain score from baseline at Day 29 will use the 'Adolescents and Adults' Version for ages 14 and above at baseline, and will be based on the *CFQ-R scaled scores*, as described in Appendix F. Analysis of this variable will be based on an MMRM model, similar to the analysis of the primary efficacy variable in Parts 1 and 2. Sex, the continuous baseline ppFEV1, and the continuous baseline CFQ-R respiratory domain score will be used as covariates in Parts 1 and 2. The presentation of results will also be similar.

[figure not shown]

**8.3.2.9 Multiplicity adjustment**

There will be no multiplicity adjustment to control the overall type 1 error rate for secondary efficacy variables.

### 8.3.5 Pharmacodynamic Analysis

The sweat chloride measurement for a given visit will be calculated as the mean of the non-missing sweat chloride measurements obtained on the left and right arms at that visit. If one of the two arm measurements at a time point is missing, the other will be used as the mean. A volume  $\geq 15$   $\mu\text{L}$  is required for an accurate determination of sweat chloride. Any results reported as having volume  $< 15$   $\mu\text{L}$  will be considered missing. Any sweat chloride values reported as  $< 10$  mmol/L or  $> 160$  mmol/L will be considered missing.

The analysis of the pharmacodynamic (PD) effect of [REDACTED] VX-440 in TC with TEZ/IVA (all parts) on sweat chloride concentrations will be described in this section. The TC groups with TEZ 100 mg qd (Cohort 1A) and 50 mg q12h (Cohort 1B) for the same dose of VX-440 will be pooled for the primary model-based analysis of sweat chloride in Part 1. [REDACTED]

Treatment groups TC-1A and TC-1B-low in Part 1 will be presented both pooled and separately, for the descriptive analysis of sweat chloride.

#### 8.3.5.1 Primary Analysis of the Dose Response trend of absolute change in sweat chloride from baseline through Day 29 (Part 1)

The null hypothesis to be tested is that the dose response of the mean absolute change from baseline through Day 29 for sweat chloride is not decreasing between placebo and the TC dose groups of Part 1, with TC-1A and TC-1B-low pooled. The test will be performed using the MCP procedure with the pre-specified contrasts provided in Section 6.2.2.1, within a linear MMRM framework using PROC GLIMMIX in SAS. The model will include treatment group, visit, and treatment-by-visit interaction as fixed effects, with continuous baseline sweat chloride as a covariate, and will include all data from all treatment groups and visits through Day 29 for analysis. The dose response test will be based on the 1-sided maximum  $t$ -statistic of the individual  $t$ -statistics for the multiple pre-specified contrasts at  $\alpha = 5\%$ , based on the treatment group means through Day 29 (Day 15 and Day 29 only), using an unstructured covariance structure for the within-subject errors. If the model estimation does not converge, a reduced compound symmetry covariance structure will be used instead.

The tabular presentation of results for the average treatment effect across visits, and the treatment effect by visit will be similar to the primary analysis of the primary efficacy variable for Parts 1 and 2. The corresponding  $p$ -value for the decreasing dose response trend will be provided.

In addition, descriptive analyses of the change from baseline will be performed for all treatment groups by post-baseline visit, with TC-1A and TC-1B-low presented both pooled and separately, for descriptive analysis.

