12.1.2.1 Pharmacodynamic Effect (Part 1)

The absolute change from baseline through Day 29 in sweat chloride is a secondary endpoint used to evaluate the PD objective of the study. In Part 1, a test for a decreasing dose-response trend between placebo and the TC dose groups will be performed using a multiple comparisons procedure (MCP). The procedure consists of testing the null hypothesis of the lack of a decreasing dose-response trend versus a decreasing trend using the 1-sided maximum *t*-statistic that controls the type I error at alpha = 5%. The procedure requires a family of candidate dose-response models to be prespecified, that covers the range of plausible and diverse dose-response profiles.

The candidate models that best describe the expected decreasing dose-response profile of the TC groups compared to placebo include a linear model, a maximum effect (E_{max}) model, and a sigmoid E_{max} model. The contrasts (i.e., linear combinations of the treatment group means through Day 29) selected to perform the MCP and that capture the shape of these candidate models are described in Table 12-3 below.

Table 12-3 Contrast Coefficients for the Multiple Comparisons Procedure in Part 1, Cohort 1B

Candidate Model	Placebo	TC-1B-low	TC-1B-high
Linear	1.0	0.0	-1.0
E _{max}	1.0	-0.5	-0.5
Sigmoid E _{max}	0.5	0.5	-1.0

E_{max}: maximum effect; TC: triple combination

Table 12-4 provides the power to detect a dose-response trend with the MCP procedure for 3 different expected dose-response profiles with a total sample size of 32 subjects in Cohort 1B assigned to TC-1B-high, TC-1B-low, and placebo in the ratio 2:1:1, based on 5000 simulations for each profile using the MCPMod R software package [Version 1.0-8].

Table 12-4 Power to Detect a Dose-response Trend Based on Change From Baseline in Sweat Chloride in Part 1, Cohort 1B

Candidate Model	Mean Change From Baseline in Sweat Chloride			Power
	Placebo	TC-1B-low	TC-1B-high	
Linear	0	-15	-20	95%
Sigmoid E _{max}	0	0	-20	99%
E _{max}	0	-20	-20	96%

E_{max}: maximum effect; TC: triple combination

Note: A 1-sided maximum *t*-statistic with a sample size of 32 subjects in Cohort 1B assigned to TC-1B-high, TC-1B-low, and placebo at a ratio 2:1:1 was used for power calculations. An SD change from baseline in sweat chloride of 13 mmol/L was used for power calculations.

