12.3.4.1 Pharmacodynamic Effect

The absolute change in sweat chloride from baseline through Day 29 is a secondary endpoint used to evaluate the PD objective of the study. The test to detect a decreasing dose-response trend of VX-440 at 2 doses in TC with TEZ/IVA relative to placebo based on sweat chloride, will be performed using the MCP procedure with the prespecified comparisons (contrasts) of the treatment group means within a linear MMRM framework. The model will include treatment group, visit, and treatment-by-visit interaction as fixed effects, with the ppFEV₁ stratification factor at randomization as a categorical covariate. The test will be performed using the 1-sided maximum *t*-statistic of the individual *t*-statistics for the multiple prespecified contrasts at alpha = 5%, based on the treatment group means through Day 29 in Cohort 1B.

[REDACTED]

Adjusted means and 95% confidence intervals of the average treatment effects through Day 29 or Week 12, as applicable, with 2-sided *P* values, for all within-group and between-group

comparisons in all parts will be estimated within MMRM, with appropriate adjustment for covariates.

Additional details of the analysis will be provided in the SAP.

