**Table 6-5 Contrast Coefficients for the Multiple Comparisons Procedure in Part 1, Cohort 1B**

Candidate Model	Placebo	TC-1B-low	TC-1B-high
Linear	1.0	0.0	-1.0
$E_{\max}$	1.0	-0.5	-0.5
Sigmoid $E_{\max}$	0.5	0.5	-1.0

$E_{\max}$ : maximum effect; TC: triple combination

Table 6-6 provides the power to detect a dose-response trend with the MCP procedure for 3 different expected dose-response profiles with a total sample size of 32 subjects in Cohort 1B assigned to TC-1B-high, TC-1B-low, and placebo in the ratio 2:1:1, based on 5000 simulations for each profile using the MCPMod R software package [Version 1.0-8].

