**Table 6-6 Power to Detect a Dose-response Trend Based on Change From Baseline in Sweat Chloride in Part 1, Cohort 1B**

Candidate Model	Mean Change From Baseline in Sweat Chloride			Power
	Placebo	TC-1B-low	TC-1B-high	
Linear	0	-15	-20	95%
Sigmoid $E_{\max}$	0	0	-20	99%
$E_{\max}$	0	-20	-20	96%

$E_{\max}$ : maximum effect; TC: triple combination

Note: A 1-sided maximum  $t$ -statistic with a sample size of 32 subjects in Cohort 1B assigned to TC-1B-high, TC-1B-low, and placebo at a ratio 2:1:1 was used for power calculations. An SD change from baseline in sweat chloride of 13 mmol/L was used for power calculations.

Table 6-7 provides the power to reject the null within-group hypothesis of no difference in the mean absolute change from baseline for sweat chloride through Day 29 (Parts 1 and 2) for any treatment group with a sample size ranging from 8 to 44 subjects per treatment group. The power calculations are based on a 2-sided 1-sample  $t$ -test at  $\alpha = 5\%$  using the PASS software package (Version 11.0), assuming a mean change of -10 to -20 mol/L and an SD of 13 mmol/L in the absolute change from baseline for sweat chloride.

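### The primary Part 1 sweat chloride trend test pools Cohorts 1A and 1B with no cohort term, while the protocol test, the contrasts and the power are for Cohort 1B

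*SAP*

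**What the plan says.** **Protocol.** Section 12.3.4.1 runs the one-sided maximum-t test at 5% "based on the treatment group means through Day 29 in Cohort 1B". The repeated-measures model has treatment, visit, their interaction and the ppFEV1 "stratification factor at randomization as a categorical covariate". Section 12.1.2.1 describes the maximum t-statistic as one "that controls the type I error at alpha = 5" percent.

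**SAP analysis text.** Section 8.3.5.1, titled as the primary analysis of the trend, tests whether the dose response "is not decreasing between placebo and the TC dose groups of Part 1, with TC-1A and TC-1B-low pooled", "using the MCP procedure with the pre-specified contrasts provided in Section 6.2.2.1". The only covariate listed is continuous baseline sweat chloride. Section 8.3.5 says that the groups sharing a VX-440 dose "will be pooled for the primary model-based analysis of sweat chloride in Part 1", and section 8.3 combines placebo subjects from all cohorts within a part.

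**SAP planning text.** The section 6.2.2.1 that supplies the contrasts concerns Cohort 1B. Table 6-5 is titled "Contrast Coefficients for the Multiple Comparisons Procedure in Part 1, Cohort 1B", and the note to Table 6-6 bases power on a test "with a sample size of 32 subjects in Cohort 1B assigned to" the three arms at 2:1:1.

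**Design.** SAP Tables 6-1 and 6-2 give Cohort 1A about 10 subjects at 4:1 with no stratification, and Cohort 1B about 32 at 2:1:1, stratified by ppFEV1. Cohort 1A is dosed first. TC-1A takes TEZ 100 mg qd, and both Cohort 1B triple-combination arms take 50 mg q12h.

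**The concern.** The protocol and the SAP name different populations and covariates for the same test. The SAP also takes contrasts and power worked out for one population and applies the contrasts to another.

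Within Cohort 1B all three arms are randomised together, so under the null the contrasts compare exchangeable groups. In the pooled analysis, half of the low-dose group and a fifth of placebo come from an earlier, separately randomised cohort that contains no high-dose subjects. The high-dose group is then compared partly with subjects who could never have been randomised to it. With no cohort term, a difference between cohorts in mean change counts as part of the dose response. The 5% level of the test and the relevance of Table 6-6 to the planned analysis are at stake.

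**Working it through.** **Inputs.** SD 13 mmol/L, one-sided 5%, and the mean profiles of SAP Table 6-6. Contrasts (placebo, low, high) from Table 6-5: linear (1, 0, -1), Emax (1, -0.5, -0.5), sigmoid Emax (0.5, 0.5, -1). Planned counts:

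| | Placebo | Low | High |
|---|---|---|---|
| Cohort 1A (4:1) | 2 | 8 | 0 |
| Cohort 1B (2:1:1) | 8 | 8 | 16 |
| Pooled | 10 | 16 | 16 |

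**Method.** For contrast c, t = Σcᵢmᵢ / (s√Σ(cᵢ²/nᵢ)), and the test uses the largest of the three. Critical values were simulated from the null distribution: 2.038 for Cohort 1B (32 - 3 = 29 df) and about 1.98 pooled (42 - 3 = 39 df). Each subject contributes one averaged outcome, a simplification of the repeated-measures model.

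**Step 1: reproduce the stated power.**

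| Profile | Stated | Cohort 1B | Pooled, no cohort difference |
|---|---|---|---|
| Linear | 95% | 94.9% | 97.7% |
| Sigmoid Emax | 99% | 99.0% | 99.7% |
| Emax | 96% | 96.4 to 96.5% | 98.9% |

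The stated figures are those of the Cohort 1B test.

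**Step 2: where a cohort difference goes.** Let d be the mean change in Cohort 1A minus that in Cohort 1B, the same in both Cohort 1A arms. The pooled placebo mean moves by (2/10)d = 0.2d, the low-dose mean by (8/16)d = 0.5d and the high-dose mean by 0.

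- Linear: 1 × 0.2d = +0.2d
- Emax: 0.2d - 0.5 × 0.5d = -0.05d
- Sigmoid Emax: 0.5 × 0.2d + 0.5 × 0.5d = +0.35d

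The pooled standard error of the sigmoid Emax contrast is 13 × √(0.25/10 + 0.25/16 + 1/16) = 4.17. At d = +10 its bias is 3.5/4.17 = 0.84 standard errors, against a critical value near 1.98.

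**Step 3: type I error.** The documents give no d, so both signs are shown. A d of 10 is 10/13 = 0.77 SD, and half the largest planned effect of 20 mmol/L.

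| d (mmol/L) | -10 | -5 | -2.5 | 0 | +2.5 | +5 | +10 |
|---|---|---|---|---|---|---|---|
| Pooled, as in the SAP | 3.1% | 3.7% | 4.2% | 5.0% | 6.3% | 7.9% | about 13% |
| Cohort 1B only | 5.0% | 5.0% | 5.0% | 5.0% | 5.0% | 5.0% | 5.0% |
| Pooled with cohort term | 5.0% | 5.0% | 5.0% | 5.0% | 5.0% | 5.0% | 5.0% |

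Here d is what remains after baseline adjustment. With the SAP's baseline covariate in the simulated model, the pooled test gives 3.1/3.7/5.0/7.8/12.7% at -10/-5/0/+5/+10. With a cohort term and d = 0, pooled power is 97.4/99.1/98.9% (linear/sigmoid Emax/Emax).

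**Step 4: the omitted stratum.** In Cohort 1B with balanced strata and an assumed difference in mean change between strata of 5 or 10 mmol/L, leaving the stratum out lowers type I error to 4.6% or 3.6%. Power becomes 94.4/98.8/96.0% or 92.9/98.4/94.9%.

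**The case against.** Pooling by VX-440 dose is deliberate, stated throughout SAP 8.3, and fixed before the first interim data cut (SAP 3). The protocol calls its statistical section a summary and leaves further detail to the SAP. Its synopsis and section 12.1.2.1 place the trend test in Part 1 without limiting the population. The cohorts share genotype, age and ppFEV1 criteria, the Day 15 and Day 29 visits and a central sweat laboratory. TC-1A and TC-1B-low share VX-440 and IVA doses and the total daily TEZ dose. The test is of a secondary endpoint in Phase 2, and no visible decision rule depends on it.

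Most of this stands and limits the weight of the point. It does not settle the conflict. Where the protocol sets out this analysis, it names Cohort 1B and the stratum. Prespecifying the pooling does not make the comparison fully randomised, and similar entry criteria make a large d less likely without making it zero.

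Four stronger readings are tempting, and the documents do not support them.

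- *The departure is unexplained.* Text next to the relevant sentences in Protocol 12.3.4.1 and SAP 8.3 and 8.3.5 is redacted, and nothing is visible between SAP 8.3.5.1 and 8.3.5.3. A rationale or a sensitivity analysis may be there. It would not change which test 8.3.5.1 calls primary.
- *The type I error is inflated.* That needs a positive d. With a negative d the test is conservative.
- *A shift confined to TC-1A also inflates the error.* Rejection is then 7.5/5.6/6.0/8.6% at -10/-5/+5/+10, but such a shift may be a real effect of the TC-1A regimen. At negative values it is a true fall in sweat chloride. These rates are not type I error.
- *Power is overstated, or omitting the stratum biases the test.* Pooled power is higher than stated, and the omission is at most mildly conservative.

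**Conclusion.** The point holds in a limited form. SAP 8.3.5.1 and Protocol 12.3.4.1 specify different primary trend tests, and SAP Tables 6-5 and 6-6 belong to the protocol's version. As the SAP is written, the 5% level holds only if the two cohorts have the same mean change after baseline adjustment, which randomisation does not ensure. Over an assumed range of ±10 mmol/L the level runs from about 3% to 13%; over ±2.5 it is 4.2% to 6.3%. The size and sign of any real difference are unknown.

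The figures assume exact allocation, no dropout, SD 13 and one averaged outcome per subject. The finding concerns this test only, not the ppFEV1 or CFQ-R models. It should be corrected, but it does not undermine the trial.

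**What to change.** Before the Part 1 data cut, after which the study team is unblinded to the Part 1 results (SAP 9.1), reconcile SAP 8.3.5.1 with Protocol 12.3.4.1:

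1. Make the Cohort 1B maximum-t test primary, with the Table 6-5 contrasts and the ppFEV1 randomisation stratum. Baseline sweat chloride may stay as a covariate.
2. Report the pooled Part 1 test as supportive, with a cohort term.

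This is a wording change in one section and needs no new data. Against the pooled test it costs about 1 to 3 points of power. If stratum and baseline explained no variance, Cohort 1B power would be 94.1/98.7/95.8% against 97.4/99.7/98.7% for the pooled test with its baseline covariate, still close to the stated 95/99/96%. Cohort 1A data stay in the supportive test and the descriptive tables.

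If the sponsor keeps the pooled test as primary, it should add a cohort term, report the Cohort 1B test as a sensitivity analysis, and state that Table 6-6 refers to Cohort 1B only. The cohort term holds the level at 5.0% for any additive shift, but it does not remove a shift confined to TC-1A.
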